# **PROTOCOL SUMMARY**

Title:	RESET-VT			
Objective:	The goal of this trial is to test the impact of catheter-based renal sympathetic denervation (RSDN) as an adjunctive treatment for patients with either ischemic or non-ischemic cardiomyopathy undergoing catheter ablation of ventricular tachycardia (VT). The proposed study is a prospective, multicenter, randomized control trial. Patients undergoing VT ablation will be randomized to either VT ablation alone or VT ablation + RSDN.			
Design:	This study is a prospective, multicenter, single-blinded, randomized (1:1) control trial evaluating the effectiveness of RSDN in the prevention of recurrent VT in patients with ischemic or non-ischemic ventricular dysfunction who are undergoing catheter ablation for VT. These patients will be randomized to ablation alone or ablation + RSDN. Subjects will only be eligible for this study if they are $\geq$ 18 years of age and have a history of structural heart disease (post-MI, dilated cardiomyopathy, sarcoid myopathy, hypertrophic cardiomyopathy, etc.), have an existing ICD and are planned for catheter-based VT ablation. In addition, eligible patients will have accessible renal vasculature (as determined by renal angiography). The patient will be blinded to the results of randomization. Once randomized, study group subjects will undergo a strategy of catheter-based renal sympathetic denervation + VT ablation. Follow-up will be conducted in regular intervals over a 24- month period.			
Enrollment:	Total: 202 subjects			
	Pilot Phase: 20 subjects (~10 control group, ~10 study group)			
Clinical Sites:	
 
Mount Sinai School of Medicine (PILOT)
 
Homolka Hospital, Prague, Czech Republic (PILOT)
 
Other Sites TBD (total up to 25 sites)
 
			
Time Course:	Initial enrollment: December 2012			
Renal VT Version 1.3 November 2012				

	Last enrollment: July 2013 (Pilot) Last 24-month follow-up: July 2015 (Pilot) Eligible subjects include those ≥ 18 years of age with a history of structural heart disease (post-MI, dilated cardiomyopathy, sarcoid myopathy, hypertrophic cardiomyopathy, etc.), have an existing ICD and are planned for catheter-based VT ablation. In addition, eligible patients will have accessible renal vasculature (as determined by renal angiography).				
Subject Description:					
Study Group:	In addition to VT ablation, the subjects in this group will undergo catheter-based renal sympathetic denervation.				
Control Group:	Subjects in the control group will undergo a standard procedure for catheter-based VT ablation.				
Primary Endpoint:	
 
Time to first event requiring appropriate ICD therapy for ventricular arrhythmia or Incessant VT (VT occurring below the ICD rate cut-off)
 
				
Secondary Endpoints:	
 
Appropriate ICD therapy for ventricular arrhythmia
 
Appropriate ICD Shocks ventricular arrhythmia
 
Inappropriate ICD therapy
 
All ICD therapy (Appropriate + Inappropriate)
 
A composite of Mortality, ICD storm, and Incessant VT (VT occurring below the ICD rate cut-off)
 
Number of Hospitalizations for Cardiovascular Causes.
 
Total VT burden (Number of episodes).
 
All-Cause Mortality.
 
The occurrence of ICD storm, defined as ≥3 appropriate shock therapies within 24 hours.
 
Differences in blood hormone measurements (including norepinephrine, aldosterone, renin, and BNP).
 
Differences in Cardiac parameters, including LV size (septal and free wall thickness) and mitral inflow (E&A velocity), as measured by trans-thoracic echocardiography.
 
Procedure related adverse events including, but not limited to hematomas, pseudoanuerysms, renal artery stenosis, renal impairment, thromboembolic events, stroke, pericardial bleeding including tamponade and myocardial infarction
 
Change in blood pressure
 
				

	
 
15. Development of orthostatic hypotension
 
16. Other individual complication rates including, but not limited to MI and death.
 
17. 30-day Major Complication Rate defined as death, stroke, MI or any other serious adverse events related to the treatment or procedure within the first 30 days or through hospital discharge (whichever is longer);
 
18. Procedure time
 

Primary Analytical Analysis:	Intent to treat analysis
Secondary Analytical Analysis:	Per protocol analysis
Principal Investigator:	[name]. Mount Sinai School of Medicine [name]
Site, Monitoring, and Data Management Center	Electrophysiology Clinical Research Group Mount Sinai School of Medicine [name]
Data Safety and Monitoring Board:	TBD

### **2 STUDY OBJECTIVE**

The goal of this trial is to test the impact of catheter-based renal sympathetic denervation (RSDN) as an adjunctive treatment for patients with either ischemic or non-ischemic cardiomyopathy undergoing catheter ablation of ventricular tachycardia (VT). The proposed study is a prospective, single-blind, multicenter, randomized control trial. Patients undergoing VT ablation will be randomized to either ablation alone or ablation + RSDN.

### **3** INTRODUCTION, RATIONALE

Sudden cardiac death (SCD), defined as an unexpected death from a cardiac cause occurring within  $\leq 1$  hour of the onset of symptoms, accounts for 300,000 to 400,000 deaths in the United States annually, or 5.6% of annual mortality. SCD is most commonly caused by ventricular tachy-arrhythmias, including ventricular tachycardia (VT). Several therapies exist for the prevention of VT, including implantable cardioverter-defibrillator therapy (ICD), anti-arrhythmic drug therapy (AAD), and the use of catheter based ablation.

Current guidelines recommend the use of implantable cardioverter-defibrillator (ICD) as therapy to prevent SCD in patients who have survived a prior cardiac arrest due to unstable VT or who have had a previous episode of spontaneous sustained VT. Several trials have demonstrated the efficacy of ICD therapy in preventing SCD. The MADIT II trial, a randomized trial of patients with prior myocardial infarction and left ventricular ejection fraction  $\leq$ 30%, demonstrated a 31% reduction in the relative risk of death in the defibrillator group.  However, ICD therapy does not prevent VT, and a significant proportion of patients may still experience appropriate shocks. In the Antiarrhythmics Versus Implantable Defibrillators (AVID) Trial, 60% of patients had  $\geq$ 1 appropriate ICD therapy for VT/VF during follow-up (31±13 months), and the first arrhythmia resulting in a shock during follow up was frequently identified as VT (63%). Unfortunately, these ICD shocks are associated with both a significant reduction in quality of life and increased

mortality. In a study examining quality of life in patients who had received ICD shocks, at 5.5 years post ICD implantation 19% of patients demonstrated signs of post-traumatic stress disorder. In the MADIT II trial, patients who experienced VT/VF had an increased risk of death, with a hazard ratio of 2.5. Thus, while ICDs have a clear overall mortality benefit in patients with a reduced ejection fraction, the ICD shocks themselves clearly reduce the quality-of-life of these patients and may have a negative impact on longevity.

Antiarrhythmic drugs (AADs) are another therapy available for the prevention of VT, but unfortunately they have little effect on ventricular arrhythmia recurrence, and may increase mortality when used in high-risk patients. In the OPTIC trial, 412 patients who had an ICD implanted within 21 days for inducible or spontaneously occurring VT/VF were randomized to either amiodarone plus beta-blocker, sotalol alone, or beta-blocker alone. Although patients in the amiodarone plus beta blocker group were less likely to receive shocks (HR, 0.27; 95% CI, 0.14-0.52; P<.001), shocks still occurred in 10.3% of these patients. In addition, serious adverse effects associated with amiodarone resulted in study drug discontinuation in 18.2% of patients at 1 year.

More recently, catheter ablation has emerged as a new option for the primary prevention of ICD shocks. Current guidelines recommend catheter ablation for symptomatic sustained monomorphic VT, including VT terminated by an ICD, that recurs despite AAD therapy or when AADs are not tolerated. In addition, ablation is indicated for control of VT storm refractory to drug therapy when there is a suspected trigger than can be targeted for ablation. The Substrate Mapping and Ablation in Sinus Rhythm to Halt Ventricular Tachycardia Study (SMASH-VT) randomized patients with a history of myocardial infarction who underwent defibrillator implantation for spontaneous VT or VF, to either defibrillator implantation alone or defibrillator implantation plus substrate-based catheter ablation. In patients who underwent defibrillator implantation alone 33% received ICD therapies (anti-tachycardia pacing or shocks), compared to 12% in patients who received defibrillator implantation plus substrate-based catheter ablation (Hazard ratio in the ablation group, 0.35; 95% confidence interval, 0.15 to 0.78, P=0.007). Similar results were seen in another multicenter randomized trial of similar design, VTACH. Despite the efficacy of VT ablation in these trials, there remain a significant number of patients how have recurrent arrhythmic events after catheter ablation procedures. This is particularly true in patients who present with ventricular arrhythmias refractory to anti-arrhythmic drugs and device therapies.

Thus, anti-arrhythmic drugs and catheter ablation each have limitations as sole therapies in patients at risk for recurrent ICD shocks. One adjunctive strategy under investigation is renal sympathetic denervation (RSDN). Recently, RSDN has been developed as a therapy to treat hypertension in patients resistant to anti-hypertensive drug therapy. In the Catheter-Based Renal Sympathetic Denervation for Resistant Hypertension: a multicentre safety and proof-of-principle cohort study, 45 patients with a mean office blood pressure of 177/101 mm Hg (SD 20/15), (mean 4.7 antihypertensive medications) underwent renal sympathetic denervation with radiofrequency based catheter ablation. After the procedure, these patients experienced a mean decrease in office blood pressure of -27/-17 mm Hg at 12 months, as well as a 47% reduction in renal noradrenaline spillover. In the Renal Sympathetic Denervation in Patients with Treatment-Resistant Hypertension (Symplicity HTN-2) Trial, a multi-center prospective trial that

randomized 106 patients to RSDN or medical management, at 6 months, 84% of patients who underwent renal denervation had a reduction in systolic blood pressure of 10 mm Hg or more, compared with 35% of controls (p<0.0001).

RSDN is thought to decrease blood pressure by a number of mechanisms including its ability to favorably affect whole body norepinephrine spillover and decrease central sympathetic tone. Indeed, RSDN has been shown to reduce whole body norepinephrine spillover by 42%, and efferent muscle sympathetic nerve activity by 66%. Interestingly, increased catecholamine and sympathetic activity are both important factors in the development of ventricular arrhythmias. In addition, chronic hypertension is believed to mediate pathogenesis and progression of cardiac arrhythmias via its remodeling effects on cardiac anatomy through the renin-angiotensin-aldosterone system.

Logically, RSDN may be an effective therapy in the prevention of SCD from VT. Interestingly, there is at least one case report examining the impact of RSDN for the treatment of recurrent appropriate ICD shocks; two patients with ICDs for scar-related VT and CHF underwent RSDN for therapy resistant electrical storm.  One patient with hypertrophic cardiomyopathy had recurrent monomorphic VT despite multiple endocardial and epicardial ablations, while the second patient with dilated non-ischemic cardiomyopathy suffered from recurrent polymorphic VT, and had declined catheter ablation therapy. After undergoing RSDN, both patients experienced significantly less episodes of VT requiring ATP or shocks. Importantly, despite normal to low blood pressure at baseline, both patients maintained a stable blood pressure at 6 months of follow up post procedure.

# Rationale for RESET-VT:

Despite significant advances in the management of ventricular arrhythmias through the use of ICD therapy, AADs, and catheter-based ablation strategies, considerable challenges remain. The optimal method for the prevention of recurrent VT following catheter ablation remains unclear. RSDN may be an effective tool for preventing ventricular arrhythmias, and associated ICD therapies, by reducing central sympathetic tone, catecholamine levels, and the renin-angiotensin-aldosterone system and promoting ventricular remodelling. Although RSDN has been shown to reduce the recurrence of VT in a case report of 2 patients suffering from electrical storm, to date no large prospective randomized study has evaluated the impact of RSDN in the prevention of recurrent VT in patients following catheter ablation of VT with ischemic or non-ischemic ventricular dysfunction. This study will specifically evaluate the safety and efficacy of adjunctive RSDN in the prevention of ICD therapy in patients with ischemic or non-ischemic ventricular dysfunction who are to receive a catheter-based VT ablation.

# 4. Schedule of Treatment and Tests:

TABLE 1: SCHEDULE OF	Baseline	Procedure*	Discharge	1 month	6,12,18 & 24 months
Type of visit	Office	Hospital		Office	Office or Transtelephonic
Informed Consent	Х				
Brief History & Physical	Х			Х	
Blood Laboratory Testing: CBC, Electrolytes, BUN/Creatinine, BNP	Х				X (12, 24m)
NIH Stroke Scale	Х		Х		
Blood for Renal Hormones (OPTIONAL)	Х				X (12m)
ТТЕ	Х				X (12 m)
Renal Angiography		Х			
Ultrasound or MR/CT Angiography					X (6 m)
Randomization		Х			
Renal Sympathetic Denervation		Х			
ICD Interrogation/remote transmission	Х			Х	X
EKG	Х				X (12m)
Office BP Measurements (including orthostatic BPs)	Х			Х	X (12m)
Medications	Х		Х	Х	Х
Adverse Events		X	Х	Х	X

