# 5.2: Secondary Endpoints:

The following secondary endpoints will be assessed:

- 1) Appropriate ICD therapy for ventricular arrhythmia assessed in the full intention-to-treat patient cohort
- 2) Appropriate ICD Shocks for ventricular arrhythmia
- 3) Inappropriate ICD therapy
- 4) All ICD therapy (Appropriate + Inappropriate)
- 5) A composite of Mortality, ICD storm, and Incessant VT (VT occurring below the ICD rate cut-off)
- 6) Number of Hospitalizations for Cardiovascular Causes.
- 7) Total VT burden (Number of episodes).
- 8) All-Cause Mortality.
- 9) The occurrence of ICD storm, defined as  $\geq 3$  appropriate shock therapies within 24 hours.
- 10) Differences in blood hormone measurements (including norepinephrine, aldosterone, renin, and BNP).
- 11) Differences in BUN/creatinine measurements.
- 12) Differences in cardiac parameters, including LV size (septal and free wall thickness) and mitral inflow (E&A velocity), as measured by trans-thoracic echocardiography.
- 13) Procedure related adverse events including, but not limited to hematomas, pseudoanuerysms, renal artery stenosis, renal impairment, thromboembolic events, stroke, pericardial bleeding including tamponade and myocardial infarction.
- 14) Development of orthostatic hypotension
- 15) Changes in blood pressure
- 16) Other individual complication rates including, but not limited to MI and death.
- 17) 30-day Major Complication Rate defined as death, stroke, MI or any other serious adverse events related to the treatment or procedure within the first 30 days or through hospital discharge (whichever is longer);
- 18) Procedure time

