#### 9.1.2 **PRE-PROCEDURE MEDICATION MANAGEMENT**

After the ablation procedure, patients should receive either an antiplatelet agent (aspirin, clopidogrel, etc) or anticoagulant (warfarin, dabigatran, etc) for at least 1 week. Further decisions regarding the peri-procedural management of other cardiovascular (including anti-coagulant and anti-thrombotic agents) and non-cardiovascular medications should be as per clinical practice – but every effort should be made to maximize beta-blocker therapy, ACEI/ARB, and spironolactone therapy as per the guidelines.

[figure not shown]

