#### 9.1 **POST-PROCEDURE**

### 9.2.1 POST-PROCEDURE FOLLOW UP

- All patients will be monitored to verify vascular hemostasis prior to discharge from the hospital.
- All patients will receive either oral aspirin (81-325 mg QD) or clopidogrel (75 mg QD) or warfarin or dabigatran or rivaroxiban for at least 1 week upon discharge.
- Medication and adverse event review will be performed prior to discharge.
- Complications including vascular, stroke, heart failure etc, and presence of ventricular arrhythmias will be documented.
- NIH stroke scale will be repeat post-procedure
- ICD programming: (see below section 9.2.3)

- The total number of episodes of VT, ATP, and Shocks will be documented at all visits.
- The follow-up includes:
  - 1 Months
    - History and Physical
    - ICD interrogation (may be trans-telephonic)
    - Office BP measurements (x2) including orthostatics
    - Review of Medications and Adverse events
  - 6 Months
    - ICD interrogation (may be trans-telephonic)
    - Review of Medications and Adverse Events
    - Repeat Renal Ultrasound or MR/CT Angiography
  - $\circ$  12 Months:
    - ICD interrogation (may be trans-telephonic)
    - EKG
    - Office BP measurements (x2) including orthostatics
    - Lab tests (CBC, Electrolytes, BUN/Cr)
    - Blood for Renal Hormones (OPTIONAL)
    - BNP Level.
    - Review of Medications and Adverse Events
    - Repeat TTE
  - 18 Months:
    - ICD interrogation (may be trans-telephonic)
    - Review of Medications and Adverse Events
  - o 24 Months:
    - ICD interrogation (may be trans-telephonic)
    - Lab tests (CBC, Electrolytes, BUN/Cr)
    - BNP Level
    - Review of Medications and Adverse Events

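### Blood pressure and orthostatic readings, which supply two secondary endpoints, are scheduled only at 1 and 12 months; adding them at 6 and 24 months is cheap, and Table 1's visit-type header needs reconciling

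*Combined protocol and SAP*

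**What the plan says.** Section 5.2 lists "Development of orthostatic hypotension" as endpoint 14 and change in blood pressure as endpoint 15. It gives no assessment time for either and no criterion for the first.

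Table 1 (section 4) marks the row "Office BP Measurements (including orthostatic BPs" at baseline, 1 month and 12 months. Section 9.2.1 matches: "Office BP measurements (x2) including orthostatics" appears under 1 month and 12 months and under no other visit. At 6 months section 9.2.1 asks for "Repeat Renal Ultrasound or MR/CT Angiography" without a pressure reading, and at 24 months for blood tests without one. Adverse events and medications are reviewed at every follow-up visit.

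On visit type, Table 1 puts one header, "Office or Transtelephonic", over the 6, 12, 18 and 24 month column. In section 9.2.1 the only item marked as possibly remote is "ICD interrogation (may be trans-telephonic".

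The blood pressure evidence is in section 3. The randomized hypertension trial reports that "at 6 months, 84% of patients who underwent renal denervation had a reduction in systolic blood pressure of 10 mm Hg or more", against 35% of controls. The proof-of-principle cohort reports a mean fall of 27/17 mm Hg at 12 months. The two-patient case report in VT describes stable pressure at 6 months from a normal to low baseline.

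**The concern.** Endpoint 14 is worded as an incidence: did the condition develop? Two readings in 24 months give prevalence at two moments. A postural drop that arises after month 1 and has gone by month 12, or that first arises after month 12, meets no scheduled reading.

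Such a change is plausible here because background therapy can move. Section 9.1.2 says "every effort should be made to maximize beta-blocker therapy, ACEI/ARB, and spironolactone therapy", in line with guidelines and in both arms, and section 9.2.2 then leaves cardiovascular drugs largely to the investigator. A drop that was followed by a drug change between months 1 and 12 could look normal at month 12.

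What is at stake is how well two secondary endpoints describe the tolerability of an added procedure in patients who, unlike those in the hypertension studies, are not selected for high blood pressure. The primary endpoint is not affected.

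**Working it through.** The plan states no figure on this point, so the check sets the schedule against the cited evidence.

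**1. Coverage.** Follow-up visits (Table 1, section 9.2.1): months 1, 6, 12, 18, 24. Visits with blood pressure: months 1 and 12.
- Share of visits with a reading: 2 of 5.
- Interval between the two readings: 12 − 1 = 11 months.
- Follow-up after the last reading: 24 − 12 = 12 months.

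**2. Match to the cited sources (section 3).**

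| Source | Time of blood pressure result | Reading scheduled then? |
|---|---|---|
| Proof-of-principle cohort, resistant hypertension | 12 months | Yes |
| Randomized hypertension trial | 6 months | No |
| Two-patient VT case report | 6 months | No |

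Two of the three sources have no matching reading in this trial.

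**3. What the other reviews can see.** Adverse-event and medication reviews at 6, 18 and 24 months can record hypotension that produced symptoms or a drug change. They cannot record a drop that nobody measured and the patient did not notice. Hypotension is also absent from the RSDN risks in the Risks section and from the examples in endpoint 13.

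**4. Effect on the comparison.** Let p1 and p0 be the true incidences in the RSDN and control arms, and s the fraction detected, assumed equal because both arms share the schedule. The expected observed difference is s·p1 − s·p0 = s(p1 − p0). With s below 1 the absolute difference shrinks, while the ratio p1/p0 is unchanged but rests on fewer cases. The documents give no value for s, p1 or p0.

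**5. Visit type at month 12.** Table 1's header allows an office or a remote visit. The same column requires office and orthostatic pressure, EKG, TTE and blood tests at 12 months, and section 9.2.1 repeats that list with only the ICD interrogation possibly remote. The header and the list conflict.

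**6. Coverage after the proposed change.** Readings at months 1, 6, 12 and 24: 4 of 5 visits. Intervals: 6 − 1 = 5, 12 − 6 = 6 and 24 − 12 = 12 months. The second year would still have one long interval, but it would end in a reading.

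**The case against.** The case against has real force.

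- **The 12-month effect is covered.** The only mean fall the protocol cites is at 12 months, when pressure is scheduled. A reader might infer that the trial largely misses the period of the effect, or measures at the wrong times. The documents do not support that: of the two cited time points, one is covered and one is not.
- **The 12-month reading is not optional.** A reader might infer from the header that month 12 can be held by telephone, leaving one reading in the whole trial. A site doing so would omit tests that the same column requires. What stands is a header that needs reconciling, not a planned loss of data.
- **The gap is not wholly unobserved.** Hypotension that led to symptoms or a drug change could surface in the reviews at 6, 18 and 24 months. What stands is the narrower gap of asymptomatic or transient drops.
- **The evidence for harm is thin.** The cited pressure effects come from resistant hypertension, and the only VT experience reports stable pressure. That weakens any expectation of a large signal. It does not make two readings an adequate measure of an endpoint the protocol chose to name.
- **A reading is not quite free.** Section 9.1.1 asks for five minutes seated and at least two readings, and the documents do not say that imaging or blood draws take place where trained staff can do this.

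**Conclusion.** This is a cheap improvement, not a flaw in the trial's main conclusion. Blood pressure and orthostatic status are measured at 2 of 5 follow-up visits, with none at 6 months and none after month 12. Incidence of orthostatic hypotension may therefore be understated, in both arms.

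The size cannot be estimated from the documents. A reader might want a count of missed cases. With 92 patients in the RSDN arm (section 7) and an assumed half of cases resolving before month 12, an assumed incidence after month 1 of 5% gives 92 × 0.05 × 0.5 = 2.3, and of 20% gives 92 × 0.20 × 0.5 = 9.2. Both rates are invented, and the sum ignores cases found at the adverse-event or medication reviews, so no such count should be relied on. The scheduling gap does not depend on it.

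The conclusion assumes that some postural drops are silent or short-lived, and that patients attend in person for the imaging at 6 months and the blood draw at 24 months. The header conflict in Table 1 stands without either assumption.

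**What to change.** 1. In Table 1 and section 9.2.1, add office and orthostatic blood pressure to the 6-month attendance, alongside the renal imaging, and to the 24-month attendance, alongside the blood draw.
2. In section 5.2, define endpoint 14 as occurrence at any scheduled reading, with the criterion for a positive reading written down, and give endpoint 15 its time points. Report how many readings each patient had, since a missed visit lowers the chance of detection.
3. Reconcile Table 1's header for the 6 to 24 month column with the tests listed beneath it and with section 9.2.1, so that it is clear which visits need attendance and which items may be remote.

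Cost: a few minutes of staff time per added reading, some local arrangement where imaging or blood is taken away from the study clinic, and less freedom to hold the 6- and 24-month visits by telephone. The change concerns endpoint measurement only and proposes nothing about drugs or clinical management.
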